4.1.2 Secondary Objectives

To evaluate the following:

- Incidence and time to mild, moderate, and severe ARDS between treatment groups
- Ventilation-free days
- Time on nasal canula or oxygen mask
- 28-day mortality— both all-cause and attributable
- ICU length of stay (in days)
- Hospitalization length of stay (in days)
- Virologic clearance rate
- Incidence of other organ disorders
- Need and duration for extracorporeal membrane oxygenation (ECMO)
- Vasopressor-free days
- Clinical improvement in chest x-rays
- Change in baseline modified Medical Research Council (mMRC) dyspnea scale
- SOFA scores assessed periodically
- Change from baseline in liver function tests (ALT, AST, and/or total bilirubin)
- Change from baseline in SCr and eGFR

¹ eGFR is calculated from the serum creatinine according to the eGFR_{CKD-EPI} equation (Levey *et al*, 2009):
$$\text{eGFR (mL/min/1.73 m}^2\text{)} = 141 \times \min(S_{\text{cr}}/\kappa, 1) \alpha \times \max(S_{\text{cr}}/\kappa, 1) - 1.209 \times 0.993 \text{Age} \times 1.018 \text{ [if female]} * 1.159 \text{ [if black], where } S_{\text{cr}} = \text{serum creatinine; } \kappa = 0.7 \text{ for females and } 0.9 \text{ for males; } \alpha = -0.329 \text{ for females and } -0.411 \text{ for males; min indicates the minimum of } S_{\text{cr}}/\kappa \text{ or } 1, \text{ and max indicates the maximum of } S_{\text{cr}}/\kappa \text{ or } 1.$$

- Change from baseline in highly-sensitive troponin (hs-troponin)
- Change from baseline ACT, aPTT, and/or PT/INR levels
- Change from baseline for antiviral immunoglobulins (IgG, IgM, and IgA) at EOS.

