4.2.2 Secondary Efficacy Endpoints

Secondary efficacy endpoints include:

- All-cause mortality
- The presence and severity of ADRS as an ordinal outcome of the proportion of patients who have none, mild, moderate, or severe ARDS
- Time to each of mild, moderate, and severe ARDS
- The number of ventilation-free days and ECMO-free days
- Time on nasal canula or oxygen mask
- Length of stay in ICU and hospital (admission to discharge)
- Virologic clearance rate
- Worst PaO₂/FiO₂ ratio following enrollment
- Change in PaO₂/FiO₂ ratio
- Vasopressor-free days
- Change from maximal radiographic damage to EOT
- Change in baseline mMRC score

- Change in APACHE II score
- Proportion of patients with extrapulmonary organ dysfunction using the daily SOFA score
- Change in liver function tests (ALT, AST, total bilirubin)
- Change in renal function tests (SCr, eGFR)
- Change in hs-troponin levels
- Change in ACT, aPTT, and/or PT/INR values
- Change in antiviral IgG, IgA, and IgM levels.

4.2.3 Health Outcomes endpoint:

- Total healthcare costs from admission to discharge between treatment groups.

4.2.4 Exploratory Endpoints:

- Change in serum cytokines including IL-1 α , IL-1 β , and ferritin levels, as well as other exploratory biomarkers drawn at the same time as LSALT peptide concentrations.
- Change in baseline antiviral immunoglobulins (IgG, IgM, IgA) at EOS.

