5.3 Discussion of Study Design

This double-blind, placebo-controlled, proof-of-concept Phase 2 study is designed to evaluate LSALT peptide compared with placebo in a defined number of adult hospitalized patients with the diagnosis of COVID-19. This is a 1:1 randomization comparing 5 mg LSALT peptide daily with matching placebo. LSALT peptide or drug-free saline will begin immediately once the patient meets all inclusion/exclusion criteria at the start of hospitalization and followed with physical and respiratory exams, blood chemistries, coagulation, hematology, ECGs, SARS-CoV-2 tests, CXRs, biomarkers, and PK will be recorded periodically throughout the 28 day study. When clinically indicated, questionnaires (APACHE II, SOFA) will be obtained at Baseline, EOT, and EOS; venous blood gas (VBG) or HCO_3 (bicarbonate) levels may be substituted for arterial blood gas (ABG) if it is SOC or in the patient's best interest, and results in comparable APACHE II and SOFA scores (Brown *et al*, 2016). Other questionnaires (Berlin Definition and modified Medical Research Council Dyspnea Scale) will be assessed at Baseline, Day 3, EOT, and EOS. Patients will be maintained on SOC, including prophylaxis or treatment for VTE, per institutional guidelines throughout the study. Dosing will end on Day 14, or at cure or increasing severity of ARDS, or at death. Patients will be followed clinically, and safety and efficacy measures will be recorded at end of study (EOS; Day 28) or death, whichever occurs first.

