5.4.3 Removal of Patient from Therapy

Reasons for permanent discontinuation of treatment include the following:

- Patient experiences two or more Grade 2 toxicities or one or more Grade 3 or 4 toxicity considered by the PI to be associated with LSALT peptide treatment (CTCAE v5.0, 2017)
- Patient requests to discontinue treatment or patient withdrawal of consent
- PI considers that it is not in the best interest of the patient to continue treatment due to an adverse event.
- Protocol deviation requiring discontinuation of study treatment for safety reasons, and/or
- Pregnancy.

Patients who discontinue treatment for any reason (except withdrawal of consent from study participation) will not be discontinued from the study and will continue to be followed for all

assessments until Day 28, or if not possible then for all assessments necessary to determine the value of the primary endpoint at Day 28.

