7.3.2.5 Pulmonary Assessments

Chest x-rays will be obtained at Baseline, Day 3, at time of clinical improvement, at EOT, at EOS, and where clinically indicated. All x-rays will be recorded in the eCRF. Chest CT will be obtained as per clinical practice at the study site.

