8.2.5 End of Treatment (EOT)

The EOT visit refers to the completion of the last dose of study drug. All study assessments outlined during the Treatment Period are to be performed. For a complete list of assessments, refer to the Study Flow Chart.

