9.3.4.3 Vital Signs, ECG, and Chest X-rays

Vital signs, 12-lead ECG parameters, and chest x-rays will be summarized using descriptive statistics by treatment including changes from baseline.

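### The chest x-ray efficacy endpoint starts from a worst film that can fall after randomisation, so it can credit deterioration followed by recovery

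*Combined protocol and SAP*

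**What the plan says.** Section 4.2.2 lists "Change from maximal radiographic damage to EOT" among the secondary efficacy endpoints. The Synopsis and Section 7.1.2 repeat it. None of the three gives a film score, a reader, or the window over which the maximum is sought.

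The matching objective in Section 4.1.2 is "Clinical improvement in chest x-rays", with no reference point.

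On film timing, Section 7.3.2.5 states: "Chest x-rays will be obtained at Baseline, Day 3, at time of clinical improvement, at EOT, at EOS, and where clinically indicated". Section 5.1 places the Day 1 film before the first dose. All the others follow the start of dosing.

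On EOT, Section 8.2.5 states: "The EOT visit refers to the completion of the last dose of study drug". The flow chart in Section 8.1 gives its day as variable. Section 5.3 states: "Dosing will end on Day 14, or at cure or increasing severity of ARDS, or at death". Section 5.4.3 opens its list with "Reasons for permanent discontinuation of treatment include the following", and worsening ARDS is not among the items that follow.

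A baseline-anchored film summary is planned only in the safety analysis, where Section 9.3.4.3 says that "chest x-rays will be summarized using descriptive statistics by treatment including changes from baseline". Section 9.3.2 leaves precise endpoint definitions to a SAP to be finalised before unblinding. The document reviewed contains no separate SAP text.

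**The concern.** A change score should start from a value that treatment cannot have affected. Here the starting value is the worst film, and four of the five planned film times (Day 3, clinical improvement, EOT, EOS), plus any clinically indicated film, come after dosing begins. The trial tests prevention of organ injury, so a drug that works should lower that worst film. Lowering it also reduces the room left to improve. A patient who is spared deterioration can then score below one who deteriorated and recovered.

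The end of the interval is not fixed either. EOT is the last dose, and on the wording of Section 5.3 worsening ARDS can bring that dose forward. The same clinical course can then score differently depending on when dosing stopped.

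At stake is the interpretation of one secondary endpoint: a between-arm difference on it could not be read as benefit or harm without further information.

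**Working it through.** The plan states no figure for this endpoint, so there is nothing to reproduce. The film scores below are assumptions (higher is worse), chosen only to show how the definition behaves.

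**1. Patient scores.** Improvement from maximum = maximum − EOT. Improvement from Baseline = Baseline − EOT. The maximum is taken over films up to and including EOT.

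| Assumed course | Maximum | EOT | From maximum | From Baseline |
|---|---|---|---|---|
| Clears, never worsens: 4 to 2 | 4 | 2 | 2 | 2 |
| Worsens, returns: 4 to 8 to 4 | 8 | 4 | 4 | 0 |
| Worsens, partly returns: 4 to 8 to 5 | 8 | 5 | 3 | −1 |
| Worsens throughout: 4 to 8 | 8 | 8 | 0 | −4 |
| Unchanged: 4 to 4 | 4 | 4 | 0 | 0 |

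Two patients who deteriorated score above the one who cleared steadily. One of them ends worse than he or she began.

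**2. Floor.** If the EOT film is among those searched, maximum ≥ EOT for every patient, so the score is never negative. This holds whatever the scale. It is why 4 to 8 ties with 4 to 4.

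**3. EOT timing.** Take the course 4 to 8 to 4. If dosing ends when the film is at its worst, the score is 8 − 8 = 0. If dosing continues until recovery, it is 8 − 4 = 4.

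**4. Does this fix a direction between arms?** Let D be the reduction in the share of patients deteriorating on LSALT, s the score of a stable patient and d that of a deteriorator. The difference, LSALT minus placebo, is D × (s − d). Assume D = 0.10 and s = 2.

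- Full return by EOT (4 to 8 to 4), d = 4: 0.10 × (2 − 4) = −0.20.
- Half return (4 to 8 to 6), d = 2: 0.10 × (2 − 2) = 0.
- Little return (4 to 8 to 7), d = 1: 0.10 × (2 − 1) = +0.10.
- EOT at the worst film, d = 0: 0.10 × (2 − 0) = +0.20.

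Now let a fraction f of full-return deteriorators die and score 0, so that d = 4 × (1 − f). Section 3.2 quotes ARDS mortality of 30% (28/30-day) and 52.4% (one COVID-19 series).

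- f = 0.30: d = 2.8, difference −0.08.
- f = 0.524: d = 1.9, difference about +0.01.
- f = 0.30 with death scored −4: d = 0.70 × 4 + 0.30 × (−4) = 1.6, difference +0.04.

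The sign changes within plausible assumptions, so no direction follows.

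**5. The alternatives.** Assume the EOS film equals the EOT film. Baseline-to-EOS improvement is then the last column above: steady clearing (2) ranks above return to baseline (0), and net worsening is negative. For Baseline to the worst scheduled later film, assume that the clearing patient's Day 3 film is still 4 and that the deteriorator's peak falls on a scheduled film. The scores are 4 − 4 = 0 and 4 − 8 = −4, again in the right order.

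**The case against.** **The definition is deferred.** Section 9.3.2 leaves details to the SAP, which could set the window and the rule for deaths. That stands for the window, the scale and death. It does not remove the starting point, which the protocol already names as the maximum. Deferral also means that the change can still be made before unblinding.

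**The endpoint matches its objective.** Improvement in films is about resolution, and a change from the worst film is a reasonable measure of that. This stands, and it is why the measure is worth keeping descriptively. It does not make the measure suitable as the only efficacy film endpoint in a prevention trial.

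**Other endpoints cover deterioration.** ARDS severity, time to ARDS, worst PaO₂/FiO₂ and ventilation-free days do so directly. This stands and sets the priority.

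**Sections 5.3 and 5.4.3 may be compatible.** The wording that opens the list in 5.4.3 is not exhaustive, so this is not a flat contradiction. The two sections still leave unclear when dosing, and therefore EOT, ends for a patient whose ARDS worsens.

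**Two stronger readings are tempting.** A reader might infer that the endpoint is biased against LSALT by a calculable amount. The documents give no film scores, no recovery pattern by EOT and no rule for deaths on this endpoint, and step 4 shows the sign turning on all three. A reader might also infer that clinically indicated films inflate the maximum in sicker patients by a known amount. The documents give neither the reading error nor the number of such films, and they schedule an additional film at clinical improvement, so improving patients gain one too.

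**Conclusion.** The point holds as a flaw in how the endpoint is built. Its starting value can be a post-randomisation outcome, so a patient who deteriorates and rebounds can rank above one who never worsens. If the maximum includes the EOT film, net worsening cannot register. The first conclusion rests on the named reference point and the film schedule. The second also needs the assumption about the window. The scores 4, 8 and 2 only illustrate.

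No between-arm direction or magnitude is claimed. The primary endpoint is unaffected. This is a low-priority improvement worth making because it is cheap.

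**What to change.** Before unblinding:

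- Define the efficacy film endpoint as change from the pre-dose Baseline film to the scheduled Day 28 (EOS) film.
- Add, as support, change from Baseline to the worst scheduled film (Day 3, EOT, EOS). Leaving out indication-driven films keeps the film times planned alike for all patients.
- Use one prespecified film score for both, and rank death worst, in line with the principle in Section 9.3.7.
- Keep maximum-to-EOT as a descriptive measure of resolution, and state the window for the maximum.
- Reconcile Sections 5.3 and 5.4.3 on when dosing, and so EOT, ends. No clinical rule is proposed here.

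The cost is endpoint and SAP wording. All the films needed are already scheduled. A film score has to be specified, but the present endpoint needs one as well. There are two downsides: the Day 28 film may lose contrast if both arms have cleared by then, and scheduled films can miss a peak between visits.

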4.2.5 Safety Endpoints

Safety endpoints include:

- Treatment-emergent adverse events (TEAEs)
- Clinical laboratory tests
- Vital signs
- Physical examinations
- 12-lead ECG
- Radiologic findings.

5 INVESTIGATIONAL PLAN

5.1 Overall Study Design and Plan – Description

This is a global, multicenter, randomized, double-blind, placebo-controlled, proof of concept study of LSALT peptide as prevention of acute respiratory distress syndrome (ARDS) and acute kidney injury in patients infected with SARS-CoV-2 (COVID-19).

After assessing the risk of ARDS and satisfying all inclusion and exclusion criteria, the patient will be randomized to 5 mg LSALT peptide or blinded placebo to be given intravenously once daily for a maximum of 14 days. Physical and respiratory examinations, vital signs, and adverse events will be recorded throughout the study, including Day 28 (EOS). Blood chemistries, hematology, coagulation, urinalysis, ECG, SARS-CoV-2 tests, eGFR, and chest x-ray (CXR) will be assessed at Day 1 (Screening/Baseline) prior to initiation of study drug, and on Day 3, EOT, and at EOS, as well as when clinically indicated. The ECG at EOS will only be obtained if

clinically indicated. An additional CXR will be obtained at time of clinical improvement. Cytokines/biomarkers and pharmacokinetics (PK) will be assessed at Day 1 (Screening/Baseline) prior to initiation of study drug, and on Days 1, 3, and EOT at 1 (mid-dose) and 2 hours (end of infusion) of drug therapy, and a single blood sample at EOS for cytokines/biomarkers only. Where applicable, a urinary pregnancy test will be obtained at Screening in women of childbearing potential. When clinically indicated, questionnaires (APACHE II, SOFA) will be obtained at Baseline, EOT, and EOS; venous blood gas (VBG) or HCO₃ (bicarbonate) levels may be substituted for arterial blood gas (ABG) if it is standard-of-care (SOC) or in the patient's best interest, and results in comparable APACHE II and SOFA scores (Brown et al, 2016). Other questionnaires (Berlin Definition and modified Medical Research Council Dyspnea Scale) will be assessed at Baseline, Day 3, EOT, and EOS. IgG, IgA, and IgM antiviral antibodies will be collected at Baseline and EOS. Patients will be maintained on the SOC per institutional guidelines, including prophylaxis or treatment of VTE, throughout the study.

Patients will be randomized to one of two blinded treatment regimens:

1. 100 mL of 5 mg IV LSALT peptide infusion over 2 hours daily
2. 100 mL of drug-free IV saline infusion over 2 hours daily.

Duration of therapy will be a maximum of 14 days. Patients will be maintained on the standard of care (SOC) for the treatment of COVID-19 as defined by institutional guidelines and/or physician practice. Co-morbidities and concomitant medications will be reviewed daily and documented in the patient's eCRF. The risk of venous thromboembolism (VTE), a potential consequence of SARS-CoV-2 infection, will be assessed and prophylaxis will be included as SOC for every patient (Zhai et al, 2020; Klok et al, 2020). Please refer to antithrombotic therapy in patients with COVID-19 (COVID-19 Treatment Guidelines Panel, Antithrombotic Therapy in Patients with COVID-19, p197; 17-December-2020).

5.2 Number of Patients (Planned)

Thirty (30) patients will be randomized to active drug (LSALT peptide) and 30 patients will be randomized to matching placebo. Patients and, if necessary, the Legal Authorized Representative (LAR), the Investigational Staff, and the Sponsor and its representatives will not know the randomization schemata. The Pharmacist at the site will be unblinded and prepare drug/placebo for injection.

A Data and Safety Monitoring Board (DSMB) will evaluate patients on a continuing basis for primarily safety assessments but also the adequacy of treatment based upon clinical data of the patient, target drug concentrations, and data obtained from the AB001 PK study in healthy subjects to offer recommendations to the Sponsor. In the absence of adverse events or any safety issues during the course of study, the DSMB may recommend continuance or suspension of the study due to futility or safety issues. The DSMB will meet at least monthly if not more frequently based upon enrollment throughout the study period. Per protocol, at no time will patients be dosed for more than 14 days of therapy. The DSMB Charter will outline all processes for changes to the protocol and protocol design prior to the first patient being enrolled into study.

5.3 Discussion of Study Design

This double-blind, placebo-controlled, proof-of-concept Phase 2 study is designed to evaluate LSALT peptide compared with placebo in a defined number of adult hospitalized patients with the diagnosis of COVID-19. This is a 1:1 randomization comparing 5 mg LSALT peptide daily with matching placebo. LSALT peptide or drug-free saline will begin immediately once the patient meets all inclusion/exclusion criteria at the start of hospitalization and followed with physical and respiratory exams, blood chemistries, coagulation, hematology, ECGs, SARS-CoV-2 tests, CXRs, biomarkers, and PK will be recorded periodically throughout the 28 day study. When clinically indicated, questionnaires (APACHE II, SOFA) will be obtained at Baseline, EOT, and EOS; venous blood gas (VBG) or HCO_3 (bicarbonate) levels may be substituted for arterial blood gas (ABG) if it is SOC or in the patient's best interest, and results in comparable APACHE II and SOFA scores (Brown *et al*, 2016). Other questionnaires (Berlin Definition and modified Medical Research Council Dyspnea Scale) will be assessed at Baseline, Day 3, EOT, and EOS. Patients will be maintained on SOC, including prophylaxis or treatment for VTE, per institutional guidelines throughout the study. Dosing will end on Day 14, or at cure or increasing severity of ARDS, or at death. Patients will be followed clinically, and safety and efficacy measures will be recorded at end of study (EOS; Day 28) or death, whichever occurs first.

5.4 Selection of Study Population

5.4.1 Inclusion Criteria

Eligible patients must fulfill the following inclusion criteria:

1. Male or female hospitalized patients between 18 and 80 years of age at time of consent.
2. Clinical and laboratory diagnosis of COVID-19 infection. Patients must be positive for the SARS-CoV-2 by Real-Time Reverse Transcriptase (RT)-PCR Diagnostic Panel or have an existing complication secondary to SARS-CoV-2 infection which was positive within 2 weeks of entry into the study. Further, patients must have at least two of the following three symptoms:
 - Fever (oral temperature $\geq 100.4^{\circ}\text{F}$ [$> 38^{\circ}\text{C}$]) with or without chills
 - Dyspnea or difficulty breathing (≥ 2 on mMRC dyspnea scale)
 - Nonproductive cough (Stokes *et al*, 2020),
 - Or other signs and symptoms of established complications to SARS-CoV-2 infection (*e.g.*, coagulopathy, cardiomyopathy, acute kidney injury [AKI], and/or acute liver injury) within the limits of Exclusion Criteria #8.
3. Patients must present with moderate to severe illness as defined below:
 - Moderate illness: Patients who have evidence of lower respiratory disease by clinical assessment or imaging and an oxygen saturation (SpO_2) $> 93\%$ on room air at sea level
 - Severe illness: Patients who have a respiratory frequency > 30 breaths per minute (bpm), $\text{SpO}_2 \leq 93\%$ on room air at sea level, ratio of arterial partial pressure of oxygen to fraction of inspired oxygen ($\text{PaO}_2/\text{FiO}_2$) < 300 , or lung infiltrates $> 50\%$ (COVID-19 Treatment Guidelines Panel, 2020).
4. APACHE II score < 20 or establishment of survivability of the patient beyond 48 hours

following randomization.

5. Therapies which have been shown to be beneficial and are included in standard-of-care COVID-19 treatment guidelines (e.g., those of WHO or NIH, or institutional guidelines) are permitted.
6. Sexually active women of child-bearing potential (WCBP) must be using a medically acceptable method of birth control throughout the study and for at least 1 day following the end of study, and have a negative urine pregnancy test at the Screening visit. A WCBP is defined as a female who is biologically capable of becoming pregnant. A medically acceptable method of birth control includes intrauterine devices in place for at least 3 months, surgical sterilization, or the implant (ACOG, 2020). In patients who are not sexually active, abstinence is an acceptable form of birth control and urine will be tested per protocol. Women who are of nonchild-bearing potential, i.e., post-menopause, must have this condition captured in their medical history. Pregnant women and nursing mothers are excluded from this study.
7. Patient or Legally Authorized Representative (LAR) is available and willing to give written informed consent, after being properly informed of the nature and risks of the study and prior to engaging in any study-related procedures.

5.4.2 Exclusion Criteria

The presence of any of the following excludes a patient from study enrollment:

1. Known sensitivity, allergy, or previous exposure to LSALT peptide.
2. Exposure to any investigational drug or device <90 days prior to entry into study.
3. Treatment with immunomodulators or immunosuppressant drugs, including but not limited to IL-6 inhibitors, TNF inhibitors, anti-IL-1 immunomodulators, and JAK inhibitors within five half-lives or 30 days (whichever is longer) prior to randomization and throughout the study period. However, should any of these treatments become SOC and incorporated into clinical treatment guidelines (e.g., those of WHO or NIH, or institutional guidelines), the treatment is permitted. Further, low-dose oral prednisone (≤ 20 mg/day) and inhaled steroids (e.g., for treatment of asthma) are allowed in the study.
4. Anticipated transfer to another hospital or medical center within 72 hours, which is not a study site.
5. Uncontrolled or poorly-treated active hepatitis B (HBV), hepatitis C (HepC), or HIV infection. Those subjects who are positive for HBV, HepC, or HIV but are well-controlled with low viral loads are allowed to participate in the study:
 - HBV low viral load defined as $<20,000$ IU/mL
 - HepC low viral load defined as $<800,000$ IU/mL
 - HIV low viral load defined as <5000 copies/mL.
6. Participation in another drug or device study at any time during this study, for example:
 - Ulinastatin 200,000 IU or greater (ClinicalTrials.org NCT03089957)
 - High dose intravenous Vitamin C (ClinicalTrials.org NCT042645333)

- Budesonide and formoterol (Festic *et al*, 2017)
- Bevacizumab to prevent ARDS (NCT01314066)
- Dornase alfa to reduce hypoxemia in ventilated trauma patients (Pottecher *et al*, 2020).

7. As indicated in the inclusion criteria, pregnant female patients are excluded from study. Further, female patients who are nursing are excluded from study.

8. Has any medical condition considered to be clinically significant and could potentially affect patient safety or study outcome, including but not limited to:

- Acute kidney injury (Thomas *et al*, 2015) or chronic kidney disease (stage-4 and stage-5 renal impairment [Wongrakpanich *et al*, 2017; Agarwal, 2016]; hemodialysis or eGFR < 30 mL/min/1.73 m²; [CKD-EPI equation; Levey *et al*, 2009])
- End-stage malignancy undergoing treatment
- Immunocompromised patients or those with medical/surgical conditions (*e.g.*, solid organ transplantation) which require chronic immunosuppression
- Chronic hematologic disease which, in the opinion of the PI, prohibits the patient from entering into study
- Acute liver injury with AST and/or ALT levels greater than 3x ULN, unless recent injury (within 2 weeks) likely due to COVID-19 infection
- History of coagulopathy of unknown etiology, as defined by abnormal ACT (only if part of SOC), aPTT, and/or PT/INR values at least 2-fold outside normal limits, and currently present at screening, and/or
- End-stage lung disease, acute lung injury, very severe chronic obstructive pulmonary disease (COPD) as assessed by the GOLD criteria (GOLD Stage IV; Vogelmeier *et al*, 2017), or mechanical ventilation.

